**Sample Size**

Sample size was calculated for a study power of 80% and an alpha of 0.05. Event rate in the control group was estimated as 40%, while that in the treated group was considered 5%. The number of resulting patients in each group is 19 for a total sample of 38 patients. This assumes a significant impact of treatment on S-IRIS-KS occurrence and its mortality.

The antiretroviral scheme will be assigned according to the criteria of the “The Antiretroviral Management Guide of Persons with HIV” in effect in Mexico.

Candidates will have an initial thorough clinical evaluation including a work-up to diagnose coinfections and rule out other neoplasms that comprise: ophthalmologic evaluation, computed tomography (CT) scan (neck, thorax, and abdomen), bone marrow culture with bone biopsy, Hepatitis B Virus (HBV) and Hepatitis C Virus (HCV) serology, venereal disease research laboratory (VDRL) test and if indicated lumbar puncture to rule-out neurosyphilis, Histoplasma urinary antigen and serology, and GenXpert MTB/RIF test. Upper gastrointestinal tract (GIT) endoscopy with biopsy of lesions; colonoscopy will be performed only on patients with diarrhea or lower-GIT bleeding. Biopsies of enlarged lymph nodes will be obtained and processed for histopathological analysis and culture. If indicated, bronchoscopy with bronchoalveolar lavage (BAL) will be performed as well as a thoracic Gallium 67 Spect-CT Scan or PET-FDG scans.

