### **Primary outcome:**

Mortality by all causes at end of follow-up, 48 weeks, adjusted at least by age, gender, CD4, and viral load of HHV-8, primarily with a survival analysis by a Cox regression, but also with a logistic regression model.

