**Statistical analysis:**

The primary analysis is going to be as intention to treat, but as a secondary analysis also as per protocol analysis is going to be performed for mortality, and S-IRIS-KS.

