**TITLE: Valganciclovir Four Weeks Prior to cART
Initiation Compared to Standard Therapy for
Disseminated Kaposi Sarcoma**

NCT number: 03296553

DATE: November 30, 2019.

Statistical analysis

Sample size was calculated for a study power of 80% and an alpha of 0.05, with an estimated event rate (IRIS) in the control group of 40%, and in the treated group of 5%. The number estimated in each group was 19, for a total sample of 38 patients.

Descriptive statistics were performed, including the number of deaths, and episodes of S-IRIS-KS, in the CG and EG groups. Comparisons between EG and CG were performed, as intention-to-treat (ITT), and as per-protocol analysis, for the primary outcome of mortality attributed to S-IRIS-KS using Proportional-Hazard Cox models.

In addition, we compared the impact of treatment on repeated episodes of S-IRIS-KS by multivariate Poisson model and by the number of participants with at least one S-IRIS-KS event, as repeated events can occur in the same patient, and the total number of events may be due to a few very susceptible individuals.

Statistical models were adjusted by baseline CD4+, CD4+/CD8+ cell ratio, HHV-8 and HIV VL, plasmatic IL-6, CRP and by the presence of concomitant coinfections. Analyses were performed using Stata Statistical program.

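### The primary Cox analysis specifies neither its covariates, nor its test, nor a method for an event-free arm, although the planning rates imply at most about 8.55 S-IRIS-KS-attributed deaths

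*SAP*

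**What the plan says.** The SAP compares the arms "for the primary outcome of mortality attributed to S-IRIS-KS using Proportional-Hazard Cox models". Two paragraphs later it adds "Statistical models were adjusted by baseline CD4+, CD4+/CD8+ cell ratio, HHV-8 and HIV VL, plasmatic IL-6, CRP". The same sentence then ends with a seventh item: "and by the presence of concomitant coinfections". That makes seven covariates: CD4, CD4/CD8 ratio, HHV-8 viral load, HIV viral load, IL-6, CRP and coinfection. It does not say which of its models takes which covariates, or whether all enter together.

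The protocol (Primary outcome) takes all-cause death at 48 weeks as primary, "adjusted at least by age, gender, CD4, and viral load of HHV-8". It names two kinds of model for this, to be done "primarily with a survival analysis by a Cox regression, but also with a logistic regression model". Its Statistical analysis section fixes the analysis set, "The primary analysis is going to be as intention to treat", but no test.

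The SAP sizes the trial "with an estimated event rate (IRIS) in the control group of 40%, and in the treated group of 5" per cent, with 19 patients per group. The protocol (Sample Size) uses the same rates and comments "This assumes a significant impact of treatment on S-IRIS-KS occurrence and its mortality", but gives no death rate.

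Neither document says whether treatment is tested by Wald, likelihood ratio or log-rank (score). Neither gives a rule for reducing covariates, an unadjusted primary analysis, or a method for an arm with no events.

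**The concern.** There are two separate problems.

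- **Too many covariates for the events.** With about one event or fewer per parameter, the large-sample approximation behind the treatment test breaks down, and a true null is rejected too often.
- **An event-free treated arm.** If valganciclovir works as planned, the treated arm may well have no primary event. The Cox hazard ratio is then not finite and its Wald standard error is very large, so the Wald test fails just when the data favour treatment most. This does not depend on the covariates.

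Because the test is unnamed, the same data can give a positive or a negative primary result according to a choice that the plan leaves open.

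**Working it through.** **Inputs.** 19 per arm, rates 40% and 5% (labelled IRIS in the SAP), alpha 0.05, power 80%; seven SAP covariates, four protocol covariates. Alpha is taken as two-sided, which the documents do not state.

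**The plan's own figure.** Unpooled normal approximation: (1.960 + 0.842)² × (0.40×0.60 + 0.05×0.95) / 0.35² = 18.42, so 19 per group. The stated sample size reproduces.

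**Covariate count.** The lists share only CD4 and HHV-8 viral load, so their union is 7 + 4 − 2 = 9. With treatment, and coinfection as one indicator, the model has 8 parameters (SAP list) or 10 (both lists).

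**Events.** 19 × 0.40 + 19 × 0.05 = 7.6 + 0.95 = 8.55 expected IRIS cases, and 8.55 / 8 = 1.07 per parameter. These are cases, not deaths. If a share f of cases die, the same in both arms (assumed range):

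| f | Expected attributed deaths | Per parameter (8) | P(no treated-arm death) = (1 − 0.05f)^19 |
|---|---|---|---|
| 1.00 | 8.55 | 1.07 | 38% |
| 0.75 | 6.4 | 0.80 | 48% |
| 0.50 | 4.3 | 0.53 | 62% |
| 0.25 | 2.1 | 0.27 | 79% |

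**Type I error by simulation.** Set-up: 3,000 trials per setting, exponential times, censoring at 48 weeks, covariates unrelated to outcome. Assumed covariates: standard normal, except gender (90/10) and coinfection (50/50), with CD4 and CD4/CD8 ratio correlated 0.7. Nulls: 22.5% per arm (the mean of the planning rates, 38 × 0.225 = 8.55 events) and 40% per arm (38 × 0.40 = 15.2 events).

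| Covariates | LR, 8.55 events | LR, 15.2 events | Wald, 8.55 | Wald, 15.2 |
|---|---|---|---|---|
| 0 | 5.3% | 5.8% | – | – |
| 2 (HHV-8 viral load, CD4) | 6.7% | 6.1% | – | – |
| 4 (protocol minimum) | 8.0% | 7.5% | 3.5% | 6.0% |
| 7 (SAP list) | 11.9% | 9.6% | 5.9% | 8.1% |
| 9 (both lists) | 15.2% | 11.1% | 6.5% | 9.4% |

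Smaller repeat runs (1,000–2,000 trials) with seven covariates gave 11–14% for LR and mostly 6–9% for Wald, the highest being 9.7%.

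**Event-free arm.** 0.95^19 = 0.377. At 40% vs 5%, the hazard ratio was not finite in 38% of trials with no covariates and 40% with seven. Power was 34% and 35% for Wald, 83% and 81% for LR, and 81% for log-rank. Among trials with no treated-arm event, Wald rejected in 0% (no covariates) and 0.5% (seven).

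**Candidate replacements.** Prognostic here means an assumed log HR of 1 per SD for HHV-8 viral load.

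| Method | Type I error | Power, covariates unrelated | Power, HHV-8 prognostic |
|---|---|---|---|
| Log-rank | 4.2–5.6% | 81% | 79% |
| Firth Cox, two covariates, penalised LR | 4.5–6.4% | 78% | 83% |

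Coverage of the two-covariate Firth profile interval was 94–97%. With seven covariates even Firth had 8.2–8.6% type I error, so penalisation alone does not solve the first problem.

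**The case against.** Four objections have weight.

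- **The SAP never says that all seven covariates enter the Cox model.** Its adjustment sentence follows the Poisson paragraph and speaks of models in general. This stands: the first problem is conditional on that reading. The second is not.
- **The planning rates are not death rates.** A reader might infer that 8.55 is the expected event count of the primary model. The documents do not support that. It is a ceiling for attributed deaths at those rates, and all-cause deaths cannot be derived.
- **The two harms belong to different tests.** A reader might infer that the primary analysis has both doubled type I error and a collapse in power. It does not: the larger inflation is that of LR, the power loss that of Wald.
- **The simulation is simple.** It assumes proportional hazards from randomisation. Yet the protocol defines S-IRIS-KS as arising after cART starts, which in the experimental arm is week 4. A repeat with treated-arm events delayed four weeks (zero or two covariates) gave the same contrast, about 33% for Wald against 79–81% for LR. Interval coverage under that delay was not examined.

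The SAP also tabulates deaths by arm and compares patients with at least one S-IRIS-KS episode, so an event-free arm would be visible. That does not supply a primary test.

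**Conclusion.** The concern holds as a gap in the primary analysis. If all seven SAP covariates enter, type I error is about 10–14% for LR and 6–9% for Wald, given assumed covariate distributions and the planning rates applying to the primary event. Whatever the covariates, the treated arm is event-free with probability 38% at a 5% rate, and more often if not every IRIS case dies. Wald power is then about 34% where LR or log-rank has about 80%. The unnamed test therefore allows either inflated error or lost power, but not both in full.

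It would also go too far to conclude that Firth regression is clearly the better remedy. Log-rank has slightly more power when covariates are unrelated to outcome, and Firth when one is strongly prognostic. Nor does any method rescue power if few cases die: at 20% vs 2.5% (half die, assumed), power is 2% for Wald, 33% for two-covariate Firth and 40% for log-rank.

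**What to change.** State in the SAP which death endpoint is primary (the protocol's all-cause or the SAP's attributed) and one intention-to-treat test that remains valid with few events and an event-free arm. Name one of these in advance:

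- **(a)** an unadjusted log-rank test, with a Firth-penalised Cox hazard ratio and profile-likelihood interval for estimation; or
- **(b)** a Firth-penalised Cox model with treatment, log10 HHV-8 viral load and CD4 (the only covariates on both lists), tested by penalised likelihood ratio, with a profile-likelihood interval.

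State that the test and estimate stand if an arm has no event. Label the seven- or nine-covariate Cox models and the logistic model exploratory.

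The cost is SAP wording and a little analysis work. Either option departs from the protocol's minimum of four covariates, and this must be documented. Firth Cox may need software beyond the Stata that the SAP names. Log-rank gives up some power if a covariate is strongly prognostic (79%, against 83% for option b). The SAP is dated November 30, 2019 and written in the past tense. If the data had already been analysed, report the change as a post hoc re-analysis beside the analysis already done.
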